#### **Secondary and Exploratory Aims:**

 To evaluate the role of gains in Veteran marital satisfaction and emotion regulation and interpersonal skills in mediating improvement in community integration for Veterans participating in MFG-mTBI vs, those participating in a health education group with their partners.

- 4. To evaluate the role of neurocognitive functioning in moderating improvement in community integration for Veterans participating in MFG-mTBI vs, those participating in a health education group for with their partners.
- To evaluate the efficacy of MFG-mTBI-C in reducing PTSD and depressive symptoms relative to reductions observed among Veterans participating in a health education group with their partners.
- 6. To evaluate comparisons between mTBI + PTSD/CS and PTSD/CS 'only' samples,

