After the problem-solving exercise, 5 minutes are reserved for a wind-down before ending. This treatment approach differs from those that deliver information or skills in a planned sequence. Instead problems with reintegration are addressed as they occur in the course of participants' daily lives. Solutions to real time problems are generated both by the group and by the educators, drawing on their knowledge of general problem-solving and compensatory strategies keyed to specific deficits, using the rehabilitation specialists (Drs. [name] and [name]) as consultants. The solution is then implemented as homework, with assistance from the caregiver and reviewed in the next session. This approach has the advantage of ecological validity, a key aspect of rehabilitation often lacking in more formulaic interventions (Cicerone et al., 2006). To accommodate difficult schedules that often include work, school, and/or childcare, we offer participants to call-in to groups from a private space, such as a bedroom or private office, to maintain confidentiality.

**Figure 3** below describes our hypothesized model of the how participation in MFG-mTBI-C leads to improved rehabilitation outcomes both directly, and indirectly through the effects of MFG-mTBI-C on couples coping and Veteran emotion regulation and interpersonal skills. We describe below four core components of MFG-mTBI-C that are hypothesized to enable the couple to begin to reverse the multiple, adverse sequelae of combat-induced mTBI described in **Figure 1** and present selected research supporting the hypothesized direct and/or indirect paths.

[figure not shown]

Figure 3: Hypothesized Direct and Indirect Effects of Multifamily Group Treatment for Veterans with mild Traumatic Brain Injury on Couples Functioning, Veteran Social Behavior and Rehabilitation outcomes

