### **Secondary Hypotheses:**

Hypothesis 3: Improvement in community reintegration will be mediated by improvements in Couples Functioning and Veteran emotion regulation and interpersonal skills. An aim of this study is to develop a conceptual model of the therapeutic action of MFGmTBI-C. We will conduct exploratory analyses to evaluate the potential mediating role of hypothesized mediators, marital satisfaction/conflict assessed by the DAS, and Veteran emotion regulation and interpersonal skills, assessed by the DERS and Duke scales, following the approach described by Baron & Kenney (1986), which entails evaluating the bivariate associations in the model prior to multivariate modeling. If the bivariate associations between the predictor, outcome and potential mediating variable are all significant, a mediational hypothesis will be evaluated using hierarchical linear models or random effects models. For example, to evaluate the potential role of marital satisfaction in mediating improvement in community integration among couples treated with MFG-mTBI-C vs. GHE, we would enter treatment assignment and time effects in Step 1, followed by marital adjustment (DAS) efficacy in Step 2, and the interaction between marital adjustment and treatment group in Step 3. A significant main and group interaction effect for marital satisfaction would support a mediational hypothesis (Kraemer et al., 2002).

Hypothesis 4: Veterans with more intact baseline cognitive functioning will show greater improvement in community integration, emotion regulation and interpersonal skills and marital satisfaction. In order to evaluate the potential role of baseline neurocognitive status in moderating the effects of treatment, we will evaluate the interaction of baseline levels of impairment with treatment group in predicting treatment response, after controlling for imbalanced baseline prognostic factors. Preliminary analyses will be conducted to evaluate the bivariate associations between baseline neurocognitive test scores and change in primary and secondary outcomes over treatment, and multivariate—level analyses will be conduct only outcome variables with an association of at least .5 for 1+ of the neurocognitive measures, using mixed models to examine the moderating effect of neurocognition on CI and other secondary or intermediate outcomes.

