Secondary Outcomes: We calculated power for the Veteran secondary outcomes, AX (anger expression) and Duke (social support) scales for a two-sided, two-sample t-test, using the same assumptions for calculating primary outcomes and the observed correlation coefficients of .90 and .72, respectively for a two sample t-test, with alpha=0.025. Based on these assumptions, we have 94% power to detect an effect of .5 on the AX scale and 81% power to detect an effect of .5 on the Duke scale. Covariates: Due to the high degree of comorbidity in this cohort of Veterans, we have specified a number of variables for potential inclusion as covariates in our analytic models, should randomization result in an imbalance. These include Veteran (and where appropriate caregiver) physical health, substance use, service use (including starting and stopping treatment), level of depressive and post-traumatic stress symptoms, as well as usual sociodemographic (race/ethnicity, gender, age, SES) and military (e.g., number of deployments) variables. As noted above under General Approach, we will employ t-tests or Wilcoxon ranksum for continuous variables, and chi-square or Fisher's exact tests for categorical variables at baseline to identify any imbalance between groups on these variables, and will control for any imbalance by including variables that differentiate groups at conventional levels by including them in our analyses as covariates. However, as discussed, given random assignment of a sample of 180 to one of two treatment groups, we anticipate that few if any variables will differentiate between groups, and that our power analyses are conservative enough to accommodate inclusion of a limited number of covariates if necessary. Potential inclusion of covariates as "control variables" should be distinguished from inclusion of covariates for the purpose of testing exploratory mediating/moderating hypotheses as described under hypotheses 3 and 4 above.

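### Hypothesis 4 gates its moderator model on a cognition-outcome correlation with no treatment term, so the screen does not select for moderation

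*Combined protocol and SAP*

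**What the plan says.** Section 5.6, Hypothesis 4, makes two different claims.

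- **Prognostic.** It opens with "Veterans with more intact baseline cognitive functioning will show greater improvement in community integration", which names no arm. The Abstract words its third hypothesis the same way.
- **Moderation.** The next sentence sets the analysis: "we will evaluate the interaction of baseline levels of impairment with treatment group in predicting treatment response". Section 3.0 agrees, with Aim 4 reading "To evaluate the role of neurocognitive functioning in moderating improvement in community integration".

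A preliminary step then correlates baseline cognitive scores with change in the outcomes. The multivariable models are run for "only outcome variables with an association of at least .5 for 1+ of the neurocognitive measures". No reason is given for .5, and the text does not say whether the correlation is pooled over arms or taken within one.

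Hypothesis 3 has a gate of its own: "If the bivariate associations between the predictor, outcome and potential mediating variable are all significant, a mediational hypothesis will be evaluated". Its worked example adds: "A significant main and group interaction effect for marital satisfaction would support a mediational hypothesis".

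Both hypotheses stand under the heading for secondary hypotheses. However, Hypothesis 3 describes its own analyses as exploratory, and the covariates paragraph of Section 5.6 refers to "testing exploratory mediating/moderating hypotheses as described under hypotheses 3 and 4 above".

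**The concern.** Moderation is a difference between two slopes: cognition on outcome change in MFG-mTBI-C, and the same in GHE. The screen measures the strength of a single association. An outcome that cognition predicts equally well in both arms, with no moderation at all, can pass easily. An outcome for which cognition matters only in the MFG arm can fail, and the planned interaction is then never fitted. A reader of the report could take the missing model as evidence that there was no moderation. Because the pooled or by-arm choice is open, two analysts following the plan could also test different sets of outcomes.

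The Hypothesis 3 gate raises a smaller question of the same kind. It requires a significant treatment-outcome association first, although the Figure 3 text in Section 5.1 says treatment "leads to improved rehabilitation outcomes both directly, and indirectly through the effects of MFG-mTBI-C on couples coping".

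**Working it through.** The plan states no power, sample size or error rate for Hypotheses 3 or 4, so there is no figure to reproduce.

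**Inputs from the plan.** 75 couples per arm (Table 4). Attrition of 20%, one of the rates in the power section, leaves 75 x 0.8 = 60 per arm. Threshold .5. Four cognitive scores: RAVLT, Trails A, Trails B, MASC. Four outcomes: Sydney, DERS, Duke, DAS.

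**Assumptions.** All correlations and path sizes; equal outcome variance in the two arms; correlation of .4 between cognitive measures; no mean treatment effect (d = 0) unless stated.

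**1. What a pooled screen measures.** With equal arms, within-arm SD of change equal to 1 and mean difference d:

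pooled r = (r_MFG + r_GHE)/2 / sqrt(1 + d^2/4)

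- .5 in MFG, 0 in GHE, d = 0: pooled r = .25. At d = .5: .25/1.031 = .243.
- .5 and -.5: pooled r = 0, the strongest contrast of these three.
- .55 in both arms (no moderation): pooled r = .55. At d = .5: .534.

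**2. Chance that it opens, by Fisher's z.** With 120 analysed, SE = 1/sqrt(117) = .0925, and atanh(.5) = .549.

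- Pooled r = .25: (.549 - .255)/.0925 = 3.18, so about 0.07%.
- Pooled r = .55: (.549 - .618)/.0925 = -0.75, so about 77%. At d = .5, about 69%.

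Simulation agrees: 0.07%, 78% and 70%.

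**3. Pooled reading, simulated (60 per arm, 0 in GHE).**

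| r in MFG | .4 | .5 | .6 |
|---|---|---|---|
| Gate opens, one measure | 0.02% | 0.07% | 0.7% |
| Gate opens, any of four | 0.05% | 0.5% | 2.6% |
| Ungated interaction power, one measure, alpha .05 | 60% | 81% | 94% |

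The result is sensitive to the variance assumption. With equal residual rather than equal total variance, the four-measure pooled gate opens 13% of the time at r = .6 and 71% at r = .7.

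**4. Within-MFG reading, gated and ungated at the same alpha.**

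| r in MFG | .4 | .5 | .6 |
|---|---|---|---|
| One measure, alpha .0125: ungated | 39-40% | 63% | 84% |
| One measure, alpha .0125: gated | 14% | 43-44% | 77% |
| Loss, points | 24-26 | 20 | 6-7 |
| Four measures, any p < .0125: ungated | 73.5% | 91.2% | 98.6% |
| Four measures, any p < .0125: gated | 41.7% | 82.2% | 98.4% |
| Loss, points | 32 | 9 | at most 1 |

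Ranges reflect simulation error. With one measure at r = .5 in MFG, this gate opens about half the time whether the GHE correlation is .5, 0 or -.5, so it does not target moderation either.

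**5. Hypothesis 3.** Mediator = a x treatment + error; outcome = c' x treatment + b x mediator + error; a = b = .5 assumed. Total effect in SD units = (ab + c')/sqrt(1 + b^2); for c' = 0 this is .25/1.118 = .22. The comparison is a joint test of both paths, alone and behind the all-significant gate.

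| Total effect, SD | 60 per arm: ungated / gated | 75 per arm: ungated / gated |
|---|---|---|
| .22 | 77% / 21% | 86% / 26% |
| .50 | 78% / 66% | 86% / 77% |
| .60 | 78% / 73% | 86% / 84% |
| .67 | 77% / 75% | 86% / 86% |

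The plan's planning range of .5 to .7 is read here as SD units. That is an assumption, because the power section defines effect size relative to the control-group mean change.

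**The case against.** **The screen fits the hypothesis as worded.** The first sentence of Hypothesis 4 and the Abstract are prognostic, and a cognition-outcome correlation is relevant to that claim. This stands, and it means that two questions share one hypothesis. It does not rescue the screen as an entry condition for the interaction, which the next sentence and Aim 4 make the target.

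**The largest losses need a reading the plan does not state.** This also stands. A reader might infer that the plan all but rules out finding moderation. The documents do not support that, because they never say the correlation is pooled. Within MFG, with four equally predictive measures, the loss is small at r = .5 and negligible at r = .6. Strong moderation on top of strong prognosis (.8 against .2, 75 per arm) passes even a pooled screen about 43% of the time, though only because the average slope is large.

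**Hypothesis 3 asks what mediates an improvement, so requiring one is coherent.** Largely accepted. At total effects of .5 to .67 SD the gate costs about 13 to 2 points at 60 per arm, and 9 to 1 at 75. A reader might also infer that the worked example demands a mediator-by-treatment interaction. The text says only that one would count in favour of mediation.

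**The analyses are exploratory and the data remain available.** True. The measures are scheduled at all three visits (Table 5), so an ungated test could still be run. It would then be a departure from the stated rule, made after the data are seen.

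**Conclusion.** The point holds for Hypothesis 4. The final model contains the right interaction, but the rule that decides whether to fit it carries no information on a difference between arms. The firm findings are the mismatch between screen and target, and the silence on pooled or within-arm calculation.

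The size is conditional. For r = .4 to .6 in MFG and 0 in GHE, the loss is near total under a pooled screen. Under a within-MFG screen it runs from about 32 points to almost nothing. Meanwhile, equal prognosis of .55 in both arms opens the pooled gate about 70 to 78% of the time with one measure. All these figures rest on assumed correlations and 60 analysed per arm.

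Hypothesis 3 is a minor note: the loss is large only for small total effects, such as about 78% against 21% at .22 SD.

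It would be wrong to infer that the trial's main conclusions are at risk. The primary comparisons do not pass through either gate, and a gate that only withholds tests does not raise the false-positive rate. The change is worth making because it is cheap and prevents an unrun model from being read as a negative result.

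**What to change.** **Hypothesis 4**

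- Delete the .5 screen, or keep the correlations as description only and state whether they are pooled or by arm.
- Fit the treatment-by-baseline-cognition interaction for each of the four listed outcomes (Sydney, DERS, Duke, DAS). Use one cognitive measure or composite, chosen by the sponsor.
- Name that measure before any outcome data are examined. Unblinding is not a usable milestone, because Section 5.1 has the PI and the study biostatistician hold the assignment list.
- Report each interaction with a 95% CI and a stated multiplicity rule. The Bonferroni rule under General Approach is written for treatment-assignment models and is not said to cover moderator tests. Bonferroni over four outcomes gives .05/4 = .0125.
- If the prognostic claim is wanted, report the cognition main effect separately.

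**Hypothesis 3**

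- Drop the significant treatment-outcome association as a precondition.
- State that a mediator-by-treatment interaction is allowed but not required.
- Report an estimated indirect effect with a CI.

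**Cost.** Wording only, no new data, and a few more exploratory tests. At alpha .0125 and 60 per arm, power for one measure is about 40%, 63% and 84% at r = .4, .5 and .6. Testing all 4 x 4 = 16 outcome-by-measure pairs with Bonferroni would cut this to 22%, 44% and 70%, which is the reason to name one measure. A composite may do better: four measures each at .5, inter-correlated .4, give a composite correlation of 4(.5)/sqrt(4 + 12(.4)) = 2/sqrt(8.8) = .67, and about 94% power at alpha .0125.

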## **Exploratory Hypotheses:**

Using the same analytic approach outlined for Hypothesis 1, we will explore the hypotheses that Veterans with mTBI treated with 6 months of multi-family group for couples (MFG-mTBI-C) will show improvement in PTSD and depressive symptoms relative to Veterans treated with group health education (GHE) with their partners, in separate analyses. Power calculation: Our power calculations are based on pilot data from our open trial of MFG-mTBI for the primary study outcome, Veteran community integration, assessed by the Sydney Psychosocial Occupational Activity scale, and for the primary spousal outcome: caregiver burden. As we have no control group to allow us to calculate an effect size for differences in pre-post-treatment change between treatment groups, we have based our calculations on available data and calculated a range of scenarios. Our calculations assume the same mean pre-post-treatment changes on the Sydney (3.9) and Caregiver Burden Inventory (CBI) (18.0), as observed in the pilot study, and further assume that the standard deviation for the change in the control group is identical to that observed in the treatment group. The effect size is defined as (mt-mc)/mc, here mt and mc are the mean changes in the treatment and control groups respectively. The correlation between the baseline score and the follow-up score (rho) is also a factor impacting the standard deviation of the mean change, which in turn impacts the effect size associated with treatment group assignment. From the pilot study, these correlation coefficients are 0.83 and 0.84 for the Sydney and CBI. Using these data we are able to calculate power for a range of clinically significant (i.e., medium to large) effect sizes. Tables 8

and **9** below present the power calculations for each of the two outcomes based on the above assumptions for a two- sided, two-sample

Table 8: Power estimate-Veteran occupational activity

Table 9: Power estimate-Caregiver burden inventory

Effect	Attrition	N per cell	α	1-β
Liiot	7	it per cen	а	, b
Size		pre/post		
		attrition		
	. = 2.			
.5	15%	90/76	0.05	.87
.5	20%	90/72	0.05	.85
.5	2070	90/12	0.03	.00
.5	25%	90/67	0.05	.83
.6	15%	90/76	0.05	.94
	222/	00/70	0.05	
.6	20%	90/72	0.05	.92
.6	25%	90/67	0.05	.91
.0	2070	30/01	0.00	.91
.7	15%	90/76	0.05	.97
.7	20%	90/72	0.05	.96
	050/	00/07	0.05	0.5
.7	25%	90/67	0.05	.95

Effect Size	Attrition	N per cell pre/post attrition	α	1-β
.5	15%	90/76	0.05	.84
.5	20%	90/72	0.05	.81
.5	25%	90/67	0.05	.79
.6	15%	90/76	0.05	.91
.6	20%	90/72	0.05	.89
.6	25%	90/67	0.05	.87
.7	15%	90/76	0.05	.95
.7	20%	90/72	0.05	.94
.7	25%	90/67	0.05	.93

Calculated for rho = .5; Pilot rho = .833Calculated for rho = .5; Pilot rho = .839

t-test, with alpha=0.05, rho=.50 and effect sizes ranging from .5 to .7. Although attrition in the pilot study was relatively low: 10%, we have conservatively calculated power for higher rates of attrition that that observed in our pilot work: 15%, 20% and 25%, at effect sizes lower than the 1.03 effect size observed for both measures. For the Sydney, we have good power to detect an effect of .5 for Occupational activity, assuming a correlation coefficient of .5, lower than the correlation observed in the pilot study of .83 even with 2.5 times the attrition observed in the pilot study. For the CBI we have good power to detect an effect of .5, lower than the correlation observed in the pilot study of .84, even at 20% attrition, and more power at higher effect sizes or lower levels of attrition. In the unlikely scenario that a substantially lower correlation is observed (.3) along with an effect size half that observed, our power falls somewhat short of conventional standards at higher levels (25%) of attrition (i.e., .70 for Sydney and .68, with a higher correlation coefficient, lower attrition or a larger effect size we have good power to detect a medium to large effect size.

We note that a larger sample size and repeated measures at follow-up will tend to increase the correlation coefficients and reduce the variance of the change over time, most likely resulting in an increase in power. The above power calculation is based on a two-sample t-test which is the simplest form of LMM (with random intercept only) and GEE. If the imbalance between groups on key participant characteristics is minimal, as we anticipate in this randomized trial, this calculation is justified. We chose the more robust approach of using the simpler model and powering our study for a worst case scenario (compared to the effect sizes and correlations

observed in our pilot data) to cover the possibility of a more substantial imbalance, rather than basing our calculations on a more sophisticated model involving many assumptions.

Secondary Outcomes: We calculated power for the Veteran secondary outcomes, AX (anger expression) and Duke (social support) scales for a two-sided, two-sample t-test, using the same assumptions for calculating primary outcomes and the observed correlation coefficients of .90 and .72, respectively for a two sample t-test, with alpha=0.025. Based on these assumptions, we have 94% power to detect an effect of .5 on the AX scale and 81% power to detect an effect of .5 on the Duke scale. Covariates: Due to the high degree of comorbidity in this cohort of Veterans, we have specified a number of variables for potential inclusion as covariates in our analytic models, should randomization result in an imbalance. These include Veteran (and where appropriate caregiver) physical health, substance use, service use (including starting and stopping treatment), level of depressive and post-traumatic stress symptoms, as well as usual sociodemographic (race/ethnicity, gender, age, SES) and military (e.g., number of deployments) variables. As noted above under General Approach, we will employ t-tests or Wilcoxon ranksum for continuous variables, and chi-square or Fisher's exact tests for categorical variables at baseline to identify any imbalance between groups on these variables, and will control for any imbalance by including variables that differentiate groups at conventional levels by including them in our analyses as covariates. However, as discussed, given random assignment of a sample of 180 to one of two treatment groups, we anticipate that few if any variables will differentiate between groups, and that our power analyses are conservative enough to accommodate inclusion of a limited number of covariates if necessary. Potential inclusion of covariates as "control variables" should be distinguished from inclusion of covariates for the purpose of testing exploratory mediating/moderating hypotheses as described under hypotheses 3 and 4 above.

Analyses to Determine Generalizability of Results: Although the rate of refusal in the pilot study was relatively low (28.6% of caregivers of consenting patients), we will compare the baseline characteristics (e.g., age, sex, education) of the study caregiver population to those that declined participation, and will evaluate reasons for refusal using questions adapted from our Family Service Needs and Treatment Preferences Scale (FANS-[name] et al., 2009, Appendix A). Missing data and loss to follow-up are usually concerns in longitudinal studies presenting problems in interpretation with any approach. The validity of the resulting inferences depends critically on the underlying mechanism that generates the missing observation. If the mechanism for missing data is not a function of the underlying missing data, then no adjustment is necessary. Data that are missing at random will yield estimates from the likelihood-based methods that are valid and efficient, provided the model assumed for the data distribution is correct. However, when missing data are related to study treatment or outcomes of interest. parameter estimates and resulting tests on hypotheses will be biased without further adjustment. In this study, data will be stratified according to their missing pattern (e.g., early termination, late termination, and complete follow-up); variables based on these groups will be used as model covariates, allowing us to examine the effects of missing-data patterns on outoutcome measures. Overall estimates can be obtained by averaging over the missing patterns. Multiple imputations will be used if missing data rates are observed to differ across observed covariates.

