### Tests of Specific Study Hypotheses:

### **Primary Hypotheses:**

Hypothesis 1: Veterans with mTBI treated with 6 months of multi-family group for couples (MFG-mTBI-C) will show improved community integration (primary outcome), and improved anger management and use of social support (secondary outcomes) compared with those treated in a health education group without training in communication skills or compensatory strategies; Changes in the primary study outcomes (Sydney Psychosocial Reintegration Scale) from baseline for each treatment group at each time point will be examined using paired t-tests or Wilcoxon signed-rank tests as appropriate. Differences in changes in mean Sydney scores from baseline between two treatment groups will be compared using t-tests or Wilcoxon rank-sum tests as appropriate at each time point. Linear mixed models will be used to examine changes in scales over time and to examine whether the effects of MFG-mTBI-C on the Sydney and secondary Veteran outcomes (DERS and social support scales) vary with time and study sites adjusted for the time-dependent treatment, imbalanced baseline prognostic factors (if applicable), and control variables relating to combat/ injury exposure (mechanism of injury (blast vs. other), # deployments, # TBI's and degree of exposure to war zone violence/threats). In addition, Spearman correlation coefficients will be used to assess associations of changes in the Sydney with changes in Veteran symptoms from baseline at each time point and to examine whether degree of associations increases over time among Veterans treated with MFG-mTBI-C. If significant patterns over time are observed in any of these variables, mixed models will then be used to examine the effects of the variables identified on CI change over 6 months post treatment.

Hypothesis 2: Caregivers whose Veteran spouse/partners are treated with MFG-mTBI-C will show reduced burden (primary caregiver outcome) over the course of treatment and in the 6-month follow-up period relative to caregivers whose Veteran partners are treated in a health education group. The analytic plan proposed in Hypothesis 1 will be used for assessing effects of MFG-mTBI-C on changes in the CBI.

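### The power in Tables 8 and 9 does not follow from the plan's stated inputs: a two-sample t-test needs a standardised change of about 1.52 and 1.44, but the plan states 1.03 for both outcomes

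*Combined protocol and SAP*

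**What the plan says.** The power calculation is in section 5.6 of the combined protocol and SAP, under Exploratory Hypotheses. It introduces Tables 8 (Sydney) and 9 (CBI) with "below present the power calculations for each of the two outcomes based on the above assumptions for a two- sided, two-sample" and continues "t-test, with alpha=0.05, rho=.50 and effect sizes ranging from .5 to .7". A later sentence repeats the method: "The above power calculation is based on a two-sample t-test which is the simplest form of LMM". This agrees with the planned comparison under Hypothesis 1: "Differences in changes in mean Sydney scores from baseline between two treatment groups will be compared using t-tests".

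The paragraph carries over the pilot mean changes (3.9 on the Sydney, 18.0 on the CBI) and assumes equal SDs of change in the two arms. It defines the effect size as (mt-mc)/mc. It gives pilot pre-post correlations of 0.83 and 0.84, but the tables use .5. It describes the tabulated effects as being "at effect sizes lower than the 1.03 effect size observed for both measures". It then concludes: "For the Sydney, we have good power to detect an effect of .5 for Occupational activity, assuming a correlation coefficient of .5". It makes the same claim for the CBI at effect .5, up to 20% attrition, and presents the scenario as a worst case relative to the pilot.

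No SD of change or of raw scores is printed, and the divisor of 1.03 is not stated.

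**The concern.** The pilot was an open trial without a control group, as the plan itself says. So 1.03 cannot be (mt-mc)/mc or any other between-arm effect; it must be a standardised pre-post change. It is also the only standardised quantity the plan gives, so it is what a reader would use to check the tables. Used that way under the stated test, it does not return the printed power.

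The good-power statements for both primary outcomes rest on these tables, as does the claim that rho .5 is conservative. The secondary-outcome power is said to use the same assumptions. If the tables are too high, a null result could be read as evidence against an effect that the trial had limited power to detect. If 1.03 is the wrong figure, the tables may be sound, but nobody can confirm that from the plan.

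**Working it through.** **Inputs** (section 5.6, power paragraph and Tables 8-9): two-sided alpha .05; n per arm after attrition 76, 72, 67; effect e = (mt-mc)/mc = .5, .6, .7; mt = 3.9 or 18.0; rho = .5; pilot effect 1.03. The tables start from 90 per arm while the design plans 75. That is a separate matter, and the tables' own n is used here.

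**Formulas.** With mt fixed, mc = mt/(1+e), so mt-mc = mt·e/(1+e). Write R = mt / SD of change. The standardised difference is d = R·e/(1+e), which is R/3 at e = .5. The two-sample noncentrality is d·sqrt(n/2) with 2n-2 degrees of freedom.

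**Step 1: what R do the printed tables need?** One R was fitted per table, using the noncentral t (n = 76/72/67):

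| Effect | Sydney printed | R = 1.518 | CBI printed | R = 1.437 |
|---|---|---|---|---|
| .5 | .87/.85/.83 | .873/.854/.828 | .84/.81/.79 | .835/.814/.786 |
| .6 | .94/.92/.91 | .937/.924/.905 | .91/.89/.87 | .910/.895/.872 |
| .7 | .97/.96/.95 | .969/.961/.949 | .95/.94/.93 | .952/.941/.925 |

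All 18 cells agree to about half a point, so the tables do follow the (mt-mc)/mc definition. The implied SDs of change are 3.9/1.518 = 2.57 and 18.0/1.437 = 12.5. The plan prints neither.

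**Step 2: what does 1.03 give?** In general, SD of change = sqrt(SDpre² + SDpost² - 2·rho·SDpre·SDpost).

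- *1.03 = mean change / raw-score SD, equal pre and post SDs.* At rho .5 the SD of change is SD·sqrt(2(1-.5)) = SD, so R = 1.03 and d = 1.03/3 = .343. Power is .557/.534/.505 at effect .5, .658/.634/.602 at .6 and .738/.715/.683 at .7.
- *Raw-score SD, most favourable pre/post ratio.* With the scaling SD set to 1 and the other to x, the variance of change at rho .5 is 1 + x² - x. Its minimum is .75, at x = .5, so the SD of change is .866. Then d = .343/.866 = .396 and power at effect .5 is .680/.656/.625.
- *1.03 = mean change / SD of change at the pilot rho, rescaled to rho .5.* R = 1.03·sqrt(2(1-.833)) = .595, d = .198, and power is .229/.219/.207 (Sydney). With rho .839 it is .222/.213/.201 (CBI).
- *1.03 = mean change / (sqrt(2)·SD).* R = 1.03·1.414 = 1.457 and power at effect .5 is .845/.825/.797. This is within 1.5 points of the CBI column but 2.5 to 3.3 points below Sydney. It divides by the SD of change at rho = 0, which the plan does not mention.

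**Step 3: the rho .3 figures** (25% attrition, n = 67; printed .70 and .68). On the raw-SD reading the SD of change is SD·sqrt(1.4), and power is .385 at effect .5 or .398 at .515 (half of 1.03). With the Step 1 ratios the same calculation gives .69 to .71 (Sydney) and .64 to .66 (CBI).

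**Step 4: the pilot correlation.** On the raw-SD reading, SD of change = SD·sqrt(2(1-.83)) = .583·SD, or .566·SD at .84. Power at effect .5 is then .92 to .96 across the three n.

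**Step 5: a possible cause.** A one-sample formula (noncentrality d·sqrt(n), n-1 degrees of freedom) with R = 1.03 gives .840/.820/.791, .914/.898/.876 and .954/.944/.928. All nine CBI cells match within 1 point. The same formula misses every Sydney cell by 1.6 to 3.9 points (the two-sample form with the variance halved is also too low); Sydney needs about 1.08.

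**The case against.** The strongest defence is Step 1. An ordinary two-sample t-test under the plan's own effect definition reproduces every cell, given one unreported SD of change per outcome. The one-sample and two-sample formulas differ by a factor of sqrt(2) in that hidden SD, apart from small degrees-of-freedom effects, so the pattern of the tables cannot separate them. The .5 rows of Table 8 are also close to a plain two-sample result at a standardised difference of .5 (.865/.846/.819).

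Much of this stands. A reader might infer from the CBI match that the sponsor halved the variance or used a one-sample formula. The documents do not establish that: the match fails for Sydney at the stated 1.03, and the rho .3 figures do not discriminate. A reader might also infer that true power is about .50 to .56. That figure depends on one reading of an undefined number.

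Two parts do not stand. The plain d = .5 reading misses the later Sydney rows by up to about 3 points, fits no row of Table 9, and contradicts the plan's definition of effect. And the fitted ratios of 1.52 and 1.44 cannot be squared with one pilot effect of 1.03 scaled by the pre, post, pooled or change SD. The defence therefore needs SDs that the plan does not print and a meaning of 1.03 that it does not give.

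**Conclusion.** The printed power and the stated pilot effect cannot both be right on any usual standardiser. With 1.03 scaled by the pre, post, pooled or change SD, power at effect .5 and n = 76 is at most about .68, against the printed .87 and .84. With equal SDs it is about .56, and with the SD of change at the pilot rho about .22. This assumes the stated test, alpha, rho .5, effect definition and the tables' own n.

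The documents do not show whether 1.03 or the tables are wrong. A missing factor of 2 in the variance of change is a possible cause, not a proven one. Nor do they show that the trial is underpowered: on the raw-SD reading, power at effect .5 is .92 to .96 at the pilot correlation. On that reading, adequate power depends on a correlation of about .83 to .84 and is not shown at rho .5, so describing rho .5 as a worst case with good power is unsupported.

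**What to change.** - Recompute Tables 8 and 9, the two rho .3 figures and the secondary-outcome power from the actual pilot SDs. Use SD of change = sqrt(SDpre² + SDpost² - 2·rho·SDpre·SDpost) and the two-sample noncentrality (mt-mc)/(SD of change·sqrt(2/n)), with n per arm.
- Print the pilot pre and post SDs for each outcome and state what 1.03 is divided by. Correct whichever of 1.03 or the tables proves wrong.
- Reword the good-power and worst-case statements to match the result. If adequate power still depends on the pilot correlation, say so.
- Do not insert .50 to .56 as replacement values; they are conditional on an assumed divisor.

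The cost is one recalculation and a rewritten paragraph, possibly with less favourable stated power at rho .5. Enrolment and study procedures do not change.
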